#### **6.2.7. Estimands for 'The change from Baseline to Day 28 of Treatment Period 6 in the total Score of the Health Assessment Questionnaire (HAQ-DI)'**

The main estimand for the key secondary efficacy endpoint 'Change from Baseline to Day 28 of TP6 of the Total Score of the Health Assessment Questionnaire (HAQ-DI)' is defined as follows:

- Population: Of all patients with gout refractory to conventional treatment defined by the study inclusion / exclusion criteria, the analysis population will include patients who were randomized to study treatment and who were dosed (ITT population)
- Variable: Continuous variable showing change from Baseline to 6 months after start of study treatment (D28 of Treatment Period 6)
- Population-level summary: Difference in mean change from baseline in total score of the HAQ-DI questionnaire between each SEL-212 treatment group versus placebo.
- Intercurrent events:
  - o All intercurrent events (as listed in 6.1 for the primary estimand) except deaths will be considered using the treatment policy strategy
  - o For deaths, the last available value will be used (while-on-treatment strategy)

A second estimand for this key secondary efficacy endpoint will be defined similarly to the main estimand but with using the while-on-treatment strategy for all intercurrent events (as listed in 6.1 for the primary estimand).

The main and second estimands will be repeated three times, once with the population changed to the mITT, and the other with the population changed to the all randomized set, and thirdly with the population changed to the PP set.

#### **6.2.8. Estimands for 'Gout Flare incidence during Treatment Periods 1-6'**

The main estimand for the key secondary efficacy endpoint 'gout flare incidence during TP1 to 6' is defined as follows:

- Population: Of all patients with gout refractory to conventional treatment defined by the study inclusion / exclusion criteria, the analysis population will include patients who were randomized to study treatment and who were dosed (ITT population).

This document is confidential.

- Variable: Incidence of gout flare during the whole treatment period from start of treatment until end of month 6. Gout flare incidence is defined as the total number of gout flares a patient experiences in respective time period divided by the length of observation of the patient in this time period.
- Population-level summary: Difference in the incidence of gout flares between each SEL-212 treatment group versus placebo for the whole treatment period (start of treatment until end of Treatment Period 6).
- Intercurrent events:
  - o All intercurrent events (as listed in 6.1 for the primary estimand) except deaths will be considered using the treatment policy strategy
  - o For deaths, the while-on-treatment strategy will be used

A second estimand for this key secondary endpoint will be defined similarly to the main estimand but with using the while-on-treatment strategy for all intercurrent events (as listed in 6.1 for the primary estimand).

These analyses will be repeated for each background medication subgroup: i) no NSAIDs or colchicine, ii) NSAIDs no colchicine, and iii) colchicine.

The main and second estimands will be repeated three times, once with the population changed to the mITT, and the other with the population changed to the all randomized set, and thirdly with the population changed to the PP set.

#### **6.2.9. Estimands for 'Gout Flare incidence during Treatment Periods 1-3'**

The main estimand for the key secondary efficacy endpoint 'gout flare incidence during TP1 to 3' is defined as follows:

- Population: Of all patients with gout refractory to conventional treatment defined by the study inclusion / exclusion criteria, the analysis population will include patients who were randomized to study treatment and who were dosed (ITT population).
- Variable: Incidence of gout flare during the whole treatment period from start of treatment until end of month 3. Gout flare incidence is defined as the total number of gout flares a patient experiences in respective time period divided by the length of observation of the patient in this time period.
- Population-level summary: Difference in the incidence of gout flares between each SEL-212 treatment group versus placebo for the whole treatment period (start of treatment until end of Treatment Period 3).
- Intercurrent events:
  - o All intercurrent events (as listed in 6.1 for the primary estimand) except deaths will be considered using the treatment policy strategy
  - o For deaths, the while-on-treatment strategy will be used

A second estimand for this key secondary endpoint will be defined similarly to the main estimand but with using the while-on-treatment strategy for all intercurrent events (as listed in 6.1 for the primary estimand).

These analyses will be repeated for each background medication subgroup: i) no NSAIDs or colchicine, ii) NSAIDs no colchicine, and iii) colchicine.

This document is confidential.

**Statistical Analysis Plan**

Sponsor: Selecta Biosciences

Protocol No.: SEL-212/301

---

The main and second estimands will be repeated three times, once with the population changed to the mITT, and the other with the population changed to the all randomized set, and thirdly with the population changed to the PP set.

This document is confidential.

SAP Version: 1.1, 21 Feb 2023

Filing requirements: TMF

## **7. General Aspects for Statistical Analysis**

### **7.1. General Methods**

SAS® version 9.4 or higher will be used for all statistical analyses and tabulations.

In general, summaries will present data by treatment group and overall for each scheduled assessment time where appropriate.

Unless stated otherwise, descriptive summaries will include n, mean, standard deviation, median, minimum and maximum for continuous variables, and n and percent for categorical variables. If there are multiple assessments collected for the same scheduled time the first assessment post-baseline will be used. The last available assessment before start of study treatment will be used as baseline.

Adverse events and medical history will be coded according to the most recent version of Medical Dictionary for Regulatory Activities (MedDRA). Prior and concomitant medications will be coded using the most recent WHO Drug Dictionary version. The actual version of MedDRA and WHO drug used will be noted in the footnote of the respective output.

### **7.2. Key Definitions**

Baseline (of the study) is defined as the last non-missing value prior to the start date and time of the study drug. For Health questionnaires (including HAQ-DI, SF-36, and PGA), gout flare assessment, tender joint assessment and swollen joint assessment, if no assessment is available prior to the start time of the study drug, assessments post the start of study drug but on the date of first study drug administration may be considered as Baseline. Tophus status at baseline in the study will be based on IRT. Baseline of the extension period is defined as the assessment prior to first dosing on Day 0 of Treatment Period 7.

Day 0 of Treatment Period 1 is defined as the first date of study drug administration.

Overall study day will be calculated as date of event/collection – first dose date of the study.

Study day within each treatment period will be calculated as date of event/collection – first dose date at each treatment period to be consistent with protocol which defines the day of dosing in each treatment period as day 0.

### **7.3. Missing Data**

Missing data will be imputed for the primary efficacy and key secondary efficacy variables as described in Section 9.

Missing or incomplete dates in safety data: In all listings, missing or incomplete dates will be left as they have been recorded. However, for calculation and sorting based on dates and for consideration in summary tables, the following method will be used: The most conservative approach will be systematically considered (i.e. if the onset date of an AE/concomitant medication is missing or incomplete, it is assumed to have occurred during the study treatment phase (i.e. a TEAE for AEs) except if the partial onset date indicates differently). A missing/incomplete date of medical history or disease diagnosis will be assumed to have occurred before any study treatment.

Missing TEAE relationship will be imputed by 'related'.

This document is confidential.

#### **7.4. Unscheduled visits**

Unscheduled visit measurements will be included in analyses and treatment summaries in the following circumstances:

- i) If there are missing data at a scheduled visit, but data available at an unscheduled visit that occurred after the previous scheduled visit, and prior to the next scheduled visit.
  - a. In the event there are more than one unscheduled visit between the previous scheduled visit and the next scheduled visit, the closest measurement to the missed target day will be used.
  - b. If there are multiple records within the same distance from the target day, the latest record will be used.
- ii) Derivations of baseline/last-on-treatment measurements.
- iii) For all safety parameters, if there are multiple measurements within a visit window, then the record closest to the target day will be used.
  - a. In the event there are more than one unscheduled visit between the previous scheduled visit and the next scheduled visit, the closest measurement to the missed target day will be used.
  - b. If there are multiple records within the same distance from the target day, the latest record will be used.

Otherwise, data collected at unscheduled visits will be included in the data listings but will not be included in the analyses or in treatment summaries.

This document is confidential.

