
Across cohorts 1 to 17, 28 SAEs have been reported in 20 of 152 (13.2%) patients. They include 9 infusion reactions reported as related or possibly related to SEL-212. Of these 9 infusion reactions, only

3 occurred during repeat dosing of SEL-212 in cohorts 7, 13 and 17; 4 occurred in cohorts that received SEL-037 alone or SEL-037 with the lowest dose of SEL-110 (0.05 mg/mL); and 2 were due to dosing errors. All SAEs were successfully treated without complication. No study drug related SAEs or discontinuations involving gout flares, metabolic disorders, hypophosphatemia, or changes in lipid levels have been reported in the Phase 2 study SEL-212/201.

Leukopenia can be seen in patients taking high doses of rapamycin for extended periods of time. Leukopenia was reported by investigators in 11 (7.2%) and neutropenia in 6 (3.9%) of patients. One patient's neutropenia was reported as severe but not identified with a TEAE of infection. No SAEs or study drug discontinuations involving leukopenia or neutropenia have been reported.

Another TEAE seen in patients taking oral rapamycin is stomatitis (mTor Inhibitor associated stomatitis-mIAS) and was observed in the SEL-212 Phase 2 trial at a lesser rate than seen in previous clinical trials ([Peterson 2016](#)). Stomatitis or aphthous ulcers were reported in 19 (12.5%) of patients; all were mild or moderate in severity. The TEAEs categorized as stomatitis or oral lesions did not result in any SAEs, study drug discontinuations, or withdrawals. All resolved with minimal topical oral treatment of corticosteroids.

Additional TEAEs of particular interest for rapamycin are hyperglycemia, hypophosphatemia, and hypertriglyceridemia. These were reported in 5.9%, 3.9% and 17.8% of patients in the SEL-212 Phase 2 trial, respectively. These TEAEs resolved without any medical intervention, their duration was transient, and they did not result in any SAEs, study drug discontinuations, or withdrawals.

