If an infusion reaction occurs, Investigators are permitted to use concomitant medications or treatments deemed necessary to provide adequate patient care. Investigators should also utilize the infusion reaction lab kit (samples for: chemistry, hematology, coagulation, histamine, serum tryptase, and anti-uricase) provided in the Study Operations Manual to collect additional blood specimens. In the case of a Grade 3 or 4 infusion reaction occurring during an infusion, the administration of study drug should be immediately discontinued, and the affected patient should be treated according to the clinical trial site's protocol for infusion reactions (e.g., monitoring, administration of antihistamines, corticosteroids, fluids and epinephrine, as clinically indicated). The patient should be withdrawn from subsequent study drug treatment.

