#### **10.4. Laboratory Evaluations**

Laboratory data will be presented in separate tables for each laboratory test type (hematology, blood chemistry, coagulation, antibodies, lipids). Each laboratory parameter will be summarized by scheduled visit – including visits of the extension phase - and by treatment group, overall SEL-212 and total, presenting actual values and change from baseline. The values from unscheduled visits will be included in analyses according to the rules set out in Section 7.4. For the TP 7 to 12 of the extension phase additionally the change from baseline of the extension phase (D0 TP7) will be summarized. Shift tables of the number and percentage of patients below normal range (low), within normal range (normal) and above normal range (high) at each scheduled post-baseline visit of the double-blind treatment period compared to the low/normal/high categorization at baseline will be provided by treatment group on SS. Shift tables of the number and percentage of patients below normal range (low), within normal range (normal) and above normal range (high) at each scheduled visit of the double-blind treatment and the extension period compared to the low/normal/high categorization at baseline and for visits of the extension period additionally at baseline of the extension period (Day 0 TP7) will be provided by treatment group on EPS. A listing of clinically significant abnormal values in the whole study but also separately for the treatment and the extension phase will be provided in the tables section on SS and EPS, as appropriate. Biomarkers and multiomic markers assessed during the double-blind treatment phase will be summarized by treatment group on SS. Biomarkers assessed during the double-blind extension phase will be summarized by treatment on EPS. Pregnancy test results and drug screen results during the double-blind treatment phase and the extension phase will be listed on the SS, only.

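### By-visit laboratory tables leave out most unscheduled samples, and no table captures each patient's worst post-baseline value, so some out-of-range results are never counted by arm

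*SAP*

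**What the plan says.** SAP 7.4 lists the circumstances in which unscheduled measurements enter analyses and summaries.

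- **Route (i), a missing visit:** "If there are missing data at a scheduled visit, but data available at an unscheduled visit that occurred after the previous scheduled visit" and before the next scheduled visit.
- **Route (ii):** "Derivations of baseline/last-on-treatment measurements".
- **Route (iii), safety parameters:** "For all safety parameters, if there are multiple measurements within a visit window, then the record closest to the target day will be used". Ties go to the latest record.
- **Everything else:** "Otherwise, data collected at unscheduled visits will be included in the data listings but will not be included in the analyses or in treatment summaries".

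SAP 10.4 applies these rules to laboratory data. "Each laboratory parameter will be summarized by scheduled visit", extension visits included, and the low/normal/high shift tables are also by scheduled visit. Section 10.4 further plans a listing of clinically significant abnormal values, placed in the tables section, for the whole study and by phase.

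Protocol 10.7 asks sites to use an "infusion reaction lab kit (samples for: chemistry, hematology, coagulation, histamine, serum tryptase, and anti-uricase") when an infusion reaction occurs. Protocol 12.2.2.6 makes clinically significant abnormal laboratory findings in dosed patients reportable as adverse events.

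**The concern.** Scheduled safety panels are sparse, and the samples taken between them tend to be the ones prompted by a clinical event. A table that takes one value per scheduled visit does not show the largest excursion a patient had if that excursion was found off schedule.

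This matters for a product containing rapamycin. Protocol 7.6.3.2.1 names hyperglycemia, hypophosphatemia and hypertriglyceridemia as of particular interest, reports them in 5.9%, 3.9% and 17.8% of Phase 2 patients, and says of them: "These TEAEs resolved without any medical intervention, their duration was transient". A short-lived change can fall between Day 21 panels.

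At stake is whether the report can count, by arm, how many patients ever had a low or high value of a given parameter. That question does not depend on whether an investigator called the value clinically significant.

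**Working it through.** The plan gives no figure to reproduce. The check is a count of scheduled panels and a comparison of dates.

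**Scheduled panels (Protocol 7.1.2 and Appendix A).** Safety laboratory samples are due on TP1 Day 0 (before infusion), Day 21 of TP1 to TP6, and TP6 Day 28.
- Post-baseline days in the treatment phase: 6 + 1 = 7.
- The Day 21 window is +2/-1 days, so the panel falls on Days 20 to 23. In TP2 to TP5, Days 0 to 19 carry no scheduled panel.
- None of the seven is drawn after an infusion on the same day.

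**An infusion-reaction kit on Day 0 of TP2 to TP6.** Dosing is due 28 days after the previous dose, with a window of -4/+3 days.
- Day 0 of the next period therefore falls on Days 28 - 4 = 24 to 28 + 3 = 31 of the previous one.
- Distance back to the previous Day 21 target: 24 - 21 = 3 to 31 - 21 = 10 days (nominally 28 - 21 = 7).
- Distance forward to the next Day 21 target: 21 days.
- An in-window scheduled Day 21 sample is at most 23 - 21 = 2 days from its target.

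The kit is outside both Day 21 windows. SAP 7.4 does not define its windows separately, so this uses the visit windows in the schedule. Even with wider windows, an in-window scheduled sample (at most 2 days off) is closer than the kit (at least 3 days off), so the kit is not selected. It can enter a by-visit table only by standing in for a missing panel.

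**Two records in one window.** Selection ignores the value.
- Scheduled sample on Day 21, repeat on Day 22: distances 0 and 1. The Day 21 value is kept, whichever is abnormal.
- Scheduled sample on Day 20, repeat on Day 21: distances 1 and 0. The repeat is kept.
- Both on the same day: 7.4(iii) takes the latest on a tie. SAP 7.1 says that when there are several assessments for one scheduled time, the first post-baseline one is used. The two rules can give opposite answers, and the SAP does not say which prevails.

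**Where an unscheduled out-of-range value can appear**

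| Value | By-visit and shift tables | Clinically significant listing (10.4) | AE/AESI tables by arm (10.3) | Patient listings |
|---|---|---|---|---|
| Replaces a missing panel, or is closest in its window | Yes | If judged significant | If judged significant | Yes |
| Any other, judged clinically significant | No | Yes, on a plain reading | Yes, as an AE | Yes |
| Any other, not so judged | No | No | No | Yes |

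The last row is the gap. Route (ii) does not close it, because SAP 10.4 plans no last-on-treatment laboratory table. SAP 10.6, by contrast, counts patients with noteworthy QTc values during the study and during the treatment phase. Laboratory data have no such any-time count.

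**The case against.** A reader might infer that unscheduled values never reach a summary and that the worst values are hidden. The documents do not support that.

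- SAP 7.4 admits unscheduled values by three routes.
- The SAP 10.4 listing sets no scheduled-visit limit, although it does not name unscheduled values outright. SAP 10 flags unscheduled assessments in listings.
- Protocol 12.2.2.6 makes clinically significant findings adverse events whenever they are detected. Significance there typically covers findings that lead to active management, come with signs or symptoms, or lead to withdrawal, which describes many samples taken because a patient was unwell.
- SAP 10.3 summarizes TEAEs and AESIs by arm, with exposure-adjusted rate differences for the most common TEAEs and for SAEs and AESIs in at least 2% of patients.
- The Phase 2 percentages are themselves TEAE rates, so the adverse event route did capture transient changes.
- The kit as described has no lipid panel, so it would not show hypertriglyceridemia. Study glucose is specified as fasting, and kits are drawn around dosing, after steroid premedication.

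A reader might also infer bias toward no difference between arms. That is not shown. The closest-record rule can keep an abnormal value as easily as drop it, and any bias would need off-schedule excursions to be more frequent in one arm.

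The remaining objection is that one record per visit is a coherent choice for a balanced comparison, and that a worst-value table has its own weakness because unscheduled sampling may differ between arms. Both points stand. They argue for keeping the by-visit tables and showing two versions of the new one. They do not supply a count by arm for out-of-range values that the investigator did not call significant. A listing gives no percentages, and hyperglycemia and hypophosphatemia are not among the laboratory AESIs.

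**Conclusion.** The point holds in a limited form. The by-visit laboratory and shift tables use one record per scheduled visit, chosen without regard to its value. Most extra unscheduled samples stay out of them, and no planned table shows each patient's worst post-baseline result. Clinically significant values are covered elsewhere. Out-of-range unscheduled values not judged significant, and not admitted by 7.4, are not counted by arm anywhere.

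The size cannot be stated: the documents give no number of unscheduled samples, reaction kits or affected patients. What can be stated is structural: seven scheduled post-baseline panels in the treatment phase, and no route into a by-visit table for a Day 0 kit in TP2 to TP6 except replacing a missing panel. This assumes that the schedule's visit and dosing windows are kept and that the 10.4 listing includes unscheduled values.

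No efficacy result or error rate is affected. It is a reporting gap in the safety analysis that is cheap to close.

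**What to change.** 1. In SAP 10.4 add, for each laboratory parameter and each study phase, a shift table from baseline to the worst post-baseline value, once for the lowest and once for the highest, using all scheduled and unscheduled records, by arm with percentages.
2. Show a version restricted to scheduled records alongside, so that a difference caused by more frequent unscheduled sampling in one arm can be recognised.
3. State in SAP 7.4 that item (iii) and the closing exclusion of other unscheduled data apply only to by-visit summaries.
4. Reconcile SAP 7.1 with 7.4(iii), saying which rule governs repeat safety measurements.
5. State that the clinically significant listing in 10.4 includes unscheduled values.

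The cost is a few more tables and a short SAP amendment, best made before unblinding. The data are already collected and listed. Sampling, visit schedule and efficacy analyses do not change.

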## **8. Demographic, Other Baseline Characteristics and Medication**

### **8.1. Patient Disposition and Withdrawals**

Patient disposition data will be listed. Summary tables reflecting the number of patients for the following will be presented:

- Screened (or enrolled) patients
- ITT, SS, mITT, all randomized, PP and EPS patients
- Patients who complete the double-blind study treatment, i.e. TP1 to TP6
- Patients who early terminate study treatment TP1 to TP6 overall and by treatment period together with reasons
- Patients who complete during double-blind extension phase TP7, TP8, TP9, TP10, TP11, TP12
- Patients who early terminate study treatment TP7 to TP12 overall and by treatment period together with reasons for early termination
- Patients who complete the study (after finishing 12 TPs)

Screen Failure subjects will be listed with reason for failure.

A figure of the percentage of patients who discontinued the study treatment will be presented by treatment and period. Additionally, a figure of the percentage of patients who discontinued the study treatment because of the stopping rule will be presented by treatment and period.

